#### 2.5.3 Handling of intercurrent events

The primary analysis will account for intercurrent events as explained in the following:

• Participants who receive the investigational imaging agent [F]CTT1057 but do not undergo/complete the [F]CTT1057 PET/CT scan for any reason (e.g. drop out, PET camera failures, etc) will not be used for the co-primary endpoint analyses. Note that safety data for these participants will be collected after the administration of the investigational imaging agent and will be summarized.

#### 2.5.4 Handling of missing values not related to intercurrent event

This is a diagnostic study, where the co-primary endpoints are calculated on the basis of onetime imaging assessment. Missing data will not be imputed.

#### 2.5.5 Sensitivity analyses

Not applicable

#### 2.5.6 Supplementary analyses

As supplementary analyses performed for the EFF, patient-level sensitivity and region-level specificity and the corresponding 95% CIs will be obtained from a covariate-adjusted logistic regression model. Candidate covariates include categorized PSA level at baseline, diagnostic biopsy Gleason score, and categorized number of PLNs dissected as given below.

- PSA level
  - $\circ$  PSA  $\leq$  20 ng/mL
  - $\circ$  PSA > 20 ng/mL
- Gleason Score
  - Grade Group 1 Gleason score  $\leq 6$
  - Grade Group 2 Gleason score 7 (or 3 + 4 = 7)
  - Grade Group 3 Gleason score 7 (or 4 + 3 = 7)
  - Grade Group 4 Gleason score 8
  - Grade Group 5 Gleason score 9 or 10
- Number of PLNs dissected
  - $\circ$  Number of PLNs < 12
  - $\circ$  Number of PLNs >= 12

Estimates of patient-level sensitivity and region-level specificity and the corresponding 95% CIs will be obtained from the logistic regression model adjusting for covariates. The p-values from the Type III tests for each candidate covariate in the full model will be provided. The patient-level sensitivity and region-level specificity (and their 95% CIs) for each level of the covariates estimated from the full model including all candidate covariates as well as the final model including only statistically significant covariates (p-value < 0.05) will be displayed. In the case that there are no statistically significant covariates identified from the full model, patient-level sensitivity and region-level specificity (and their 95% CIs) for the unadjusted logistic regression model will be provided.

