For region-level specificity, the null hypothesis  $H_0$ : region-level specificity  $p_0 = 0.70$  will be tested against the alternative hypothesis  $H_1$ :  $p_1 > 0.70$ . Assuming a specificity of 0.85 under the alternative hypothesis, approximately 123 patients (which includes 37 patients with PLN based on 30% prevalence) would achieve 90% statistical power to detect a change in specificity of 0.15 using a one-sided binomial test at a target significance level of 2.5 %. Taking into account 20% dropout rate, 154 patients can ensure the 90% statistical power. The lower bounds of the 95% CI for specificity should be greater than 0.70 to be considered success.

The lower bound of the 95% CI for sensitivity should be greater than 0.50 and the lower bound of the 95% CI for specificity should be greater than 0.70 for the study to be considered a success.

A total sample size of 195 patients can ensure 90% statistical power for patient-level sensitivity and 99% statistical power for region-level specificity resulting in an overall study statistical power of at least 89.1% ( $0.9 \times 0.99$ ).

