#### Patient-level sensitivity

For patient-level sensitivity, the null hypothesis (H0: patient-level sensitivity p0 = 0.50) will be tested against the alternative hypothesis (H1: p1 > 0.50)Assuming a sensitivity of 0.63 under the alternative hypothesis, approximately 156 participants with primary tumor and/or metastatic PLN would achieve 90% statistical power to detect a change in sensitivity of 0.13 using a one-sided binomial test at a targeted one-sided significance level of 2.5%. Taking into account a 20% dropout rate, 195 participants can ensure the 90% statistical power.

The lower bound of the 95% CI for sensitivity should be greater than 0.50 to be considered a success.

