#### **Region-level specificity**

For region-level specificity, the null hypothesis (H0: region-level specificity p0 = 0.70) will be tested against the alternative hypothesis (H1: p1 > 0.70). Assuming a specificity of 0.85 under the alternative hypothesis, approximately 123 participants (which includes 37 participants with PLN based on a 30% prevalence) would achieve 90% statistical power to detect a change in specificity of 0.15 using a one-sided binomial test at a targeted significance level of 2.5 %. Taking into account a 20% dropout rate, 154 participants can ensure the 90% statistical power.

Novartis	Confidential	Page 37 of 43
SAP Amendment 2		Study No. CAAA405A12302

The lower bound of the 95% CI for specificity should be greater than 0.70 for the study to be considered a success.

A total sample size of 195 participants can ensure 90% statistical power for patient-level sensitivity and 99% statistical power for region-level specificity resulting in an overall study statistical power of at least 89.1% ( $0.9 \ge 0.99$ ).

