# 5.4 Statistical models

### 5.4.1 Analysis supporting primary objective(s)

Patient-level sensitivity and two-sided exact binomial 95% CIs will be calculated.

Novartis	Confidential	Page 40 of 43
SAP Amendment 2		Study No. CAAA405A12302

Only pelvic lymph node regions will be used to calculate the specificity. Region-level specificity and two-sided exact binomial 95% CIs will be calculated.

Exact binomial confidence intervals (implemented using SAS procedure FREQ with EXACT statement for one-way tables) will be calculated (Clopper and Pearson 1934).

The supplementary analyses for the co-primary endpoints of patient-level sensitivity and region-level specificity and the corresponding 95% CIs will be calculated based on a covariateadjusted logistic regression model. The LOGISTIC procedure in SAS will be used to implement the logistic regression model adjusting for covariates. This analysis will be applied to each of the three central reader via the (BY READER) statement.

The predicted probability and 100  $(1-\alpha)$ % confidence limits for patient-level sensitivity  $P_{Sens}$  for each central reader can be obtained from SAS using the logistic regression model with covariates.

$$Logit (P_{Sens}) = \log \left\{ \frac{P_{Sens}}{1 - P_{Sens}} \right\} = \alpha + \beta_1 X_{PSA} + \beta_2 X_{Gleason \, Grp \, 2} + \beta_3 X_{Gleason \, Grp \, 3} + \beta_4 X_{Gleason \, Grp \, 4} + \beta_5 X_{Gleason \, Grp \, 5} + \beta_6 X_{PLNs}$$

The predicted probability and 100  $(1-\alpha)$ % confidence limits for region-level specificity  $P_{Spec}$  for each central reader can be obtained from SAS using the logistic regression model with covariates.

 $Logit (P_{Spec}) = \log \left\{ \frac{P_{Spec}}{1 - P_{Spec}} \right\} = \alpha + \beta_1 X_{PSA} + \beta_2 X_{Gleason \, Grp \, 2} + \beta_3 X_{Gleason \, Grp \, 3} + \beta_4 X_{Gleason \, Grp \, 4} + \beta_5 X_{Gleason \, Grp \, 5} + \beta_6 X_{PLNs}$ 

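### The supplementary logistic refit on p<0.05 covariates gives level-specific CIs that under-cover, and the six-slope specificity model is too sparse for ordinary maximum likelihood

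*SAP*

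**What the plan says.** SAP 2.5.6 plans covariate-adjusted logistic models for both co-primary endpoints in the efficacy set. The candidates are PSA (two categories), biopsy Gleason grade group (five) and number of pelvic lymph nodes (PLNs) dissected (fewer than 12, or 12 and more). Type III p-values come from the full model. Level-specific estimates and CIs are shown for the full model and for "the final model including only statistically significant covariates (p-value < 0.05) will be displayed". If nothing is significant, an unadjusted logistic model is reported instead.

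SAP 5.4.1 writes out both models with the same six slopes (one PSA, four Gleason, one PLN), with Gleason 6 or below as reference, to be run in the SAS LOGISTIC procedure: "This analysis will be applied to each of the three central reader via the (BY READER) statement".

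Neither section names a penalised or exact method, a rule for separation or sparse levels, the Type III test statistic, or any allowance for the selection step. Success itself is judged elsewhere (SAP 2.5.2), by exact binomial CIs and a two-of-three-readers rule.

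**The concern.** There are two separate problems.

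- **Selection.** Keeping covariates because they reached p<0.05 and then printing ordinary 95% CIs from the same data ignores the selection. When a kept covariate is noise, its level-specific estimates have been chosen for being far apart, so the CIs miss the truth too often. Because the step runs separately by reader, the three final models may contain different covariates.
- **Sparse data.** A covariate level in which every PLN-negative unit is read negative has no finite maximum-likelihood coefficient. Eligibility is high-risk disease (Protocol 5.1), so the Gleason reference group may well be small. Protocol 4.1 calls for at least 12 dissected nodes, so the group with fewer may be small too.

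At stake is the credibility of the adjusted, level-specific sensitivity and specificity in the study report.

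**Working it through.** **Inputs from SAP 3.1.** For sensitivity: "approximately 156 participants with primary tumor and/or metastatic PLN would achieve 90% statistical power", with null 0.50 and alternative 0.63. For specificity: "Assuming a specificity of 0.85 under the alternative hypothesis, approximately 123 participants (which includes 37 participants with PLN based on a 30% prevalence", with null 0.70. Dropout is 20%.

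**Step 1: reproduce the design** (exact binomial, one-sided 2.5%).
- n = 156: attained alpha 0.0225, power 0.901.
- 123 − 37 = 86 negatives: attained alpha 0.0223, power 0.914.
- 156/0.8 = 195 and 123/0.8 = 153.75, rounded up to 154.

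All agree with the SAP. The 86 shows that its sample size counts one PLN unit per patient.

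**Step 2: events per slope** (1 + 4 + 1 = 6 slopes).

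| Model | Events | Per slope |
|---|---|---|
| Specificity, one unit per patient | 156 × 0.70 = 109; × 0.15 = 16.4 | 2.7 |
| Specificity, sides counted separately, all nodal disease bilateral | 2 × 109 = 218; × 0.15 = 32.7 | 5.5 |
| Specificity, sides counted separately, all unilateral | 312 − 47 = 265; × 0.15 = 39.8 | 6.6 |
| Sensitivity | 156 × 0.37 = 57.7 | 9.6 |

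**Step 3: how often a level has no finite estimate.** If a level holds a share f of 109 negatives, the chance that it contains no false positive is (1 − 0.15f)^109:
- f = 0.02: 0.72
- f = 0.05: 0.44
- f = 0.20: 0.036, so at most 5 × 0.036 = 0.18 over five equal Gleason levels

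Simulation of the full SAP 5.4.1 model agrees. It used 1,200–1,500 runs per scenario and no true covariate effect. Assumed, because the documents do not give them: PSA above 20 in 35%; 12 or more nodes in 50% or 85%; and Gleason mixes even, 5/20/20/30/25% and 2/13/15/40/30%. Share of fits with at least one non-finite estimate:

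| Model | Even | 5% Gleason ≤6 | 2% Gleason ≤6 |
|---|---|---|---|
| Specificity 0.85, 109 units | 16–25% | 51–53% | 74–75% |
| Specificity 0.85, 218 sides | 1% | 20% | 54–55% |
| Sensitivity 0.63, 156 patients | 0% | 6% | 35% |

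At specificity 0.95 with 109 units the rate is 87–97%. Full-model CIs cover 94–99% across these scenarios and are conservative where separation occurs.

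**Step 4: the p<0.05 step, no true effects.** With Wald Type III tests, a covariate is kept in 8–10% of specificity fits and 12–14% of sensitivity fits in these mixes. Over a wider set of assumed mixes the ranges are about 6–12% and 11–15%. Level-specific 95% CIs in those refits cover 68–78% in these mixes and about 70–84% in a repeat with other mixes. If readers were independent, at least one of three would keep a covariate in 1 − (1 − 0.085)³ = 23% of trials for specificity and 1 − (1 − 0.13)³ = 34% for sensitivity. Readers share the same scans, so these are only indicative.

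**Step 5: remedies, specificity model, 109 units.**
- Firth likelihood on all six slopes without selection: finite by construction; coverage 0.955–0.959 at specificity 0.85 and 0.93–0.95 at 0.95.
- Collapsing Gleason to ≤7 versus ≥8 under ordinary likelihood (16.4/3 = 5.5 events per slope): non-finite fits fall to 8–10% at 0.85 but remain 52–58% at 0.95. Collapsing alone is not enough.
- A standardised marginal specificity from an uncorrected Firth fit, with Gleason in three groups, averages 0.835 when the truth is 0.85 and 0.930 when it is 0.95.

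**The case against.** The best defence is that little hangs on this analysis. It is supplementary, carries no alpha, and the full model is displayed with the same covariates for every reader. Under no effect, the fallback returns the unadjusted model in about nine of ten specificity fits, and the software warns of separation. All of that stands and keeps the point minor. It does not justify a stated rule whose intervals are wrong whenever it acts.

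A reader might infer more than the documents support:

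- **Both models are equally sparse.** No. The 2.7 applies to specificity only; sensitivity has 9.6 events per slope. The 2.7 also needs one PLN unit per patient. The SAP's sample size counts that way, but SAP 1.1 describes a left/right template, and two sides per patient would give 5.5–6.6.
- **The adjusted CIs are too narrow throughout.** No. Under-coverage belongs to the selected refit; the full model errs wide where separation occurs.
- **Selection of noise is more frequent.** Likelihood-ratio tests keep a covariate in 16–19% of null specificity fits. The SAP does not name the statistic, but Wald is the usual default for Type III tests in that procedure, and it gives the lower figures.
- **Readers cannot be compared.** They can, on the full model and on the exact CIs.
- **This is the only further analysis of the co-primaries.** That cannot be established, because SAP 2.7 is absent from the public text.

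**Conclusion.** The concern holds as a minor point about two features of the supplementary analysis.

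First, the p<0.05 refit yields nominal 95% CIs that cover about 70–84% when a noise covariate is kept. That happens in roughly 6–12% of specificity fits and 11–15% of sensitivity fits, possibly with different final models by reader.

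Second, in the specificity model, ordinary maximum likelihood leaves at least one level without a finite estimate in about 20–75% of fits, or about 1–55% if two sides per patient are analysed.

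These ranges assume no true covariate effects, specificity 0.85, 156 evaluable patients and 30% nodal prevalence. They depend heavily on Gleason, PSA and node-count mixes that the documents do not give. Default maximum likelihood and Wald tests are inferred from the SAP's silence. A non-finite estimate affects the level concerned, not necessarily every estimate. Nothing here changes the co-primary decision.

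**What to change.** In SAP 2.5.6 and 5.4.1:

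1. Delete the p<0.05 final-model step and its unadjusted fallback. Report one pre-specified model, identical for all three readers.
2. Collapse the sparse Gleason levels, for example to ≤7, 8 and 9–10. This leaves four slopes, or 16.4/4 = 4.1 false positives per slope.
3. Fit by Firth penalised likelihood and give profile-likelihood CIs for the level-specific estimates.
4. Keep the raw proportion with its exact CI as the overall estimate. Do not report a standardised marginal value from the uncorrected Firth fit, which is pulled towards 0.5; if one is wanted, use an intercept-corrected version.

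The cost is SAP wording and a small programming change. The loss is detail across the lower Gleason groups, which the SAP 2.2.1 subgroup summaries still show.

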### 2.6 Analysis supporting secondary objectives

The secondary efficacy objectives are to:

- Evaluate the patient-level specificity of [F]CTT1057
- Evaluate the patient-level positive predictive value of [F]CTT1057
- Evaluate the patient-level negative predictive value of [F]CTT1057
- Evaluate the patient-level accuracy of [F]CTT1057
- Evaluate the region-level sensitivity of [F]CTT1057 for patients excluding micrometastasis
- Evaluate the region-level sensitivity of [F]CTT1057
- Evaluate the region-level positive predictive value of [F]CTT1057
- Evaluate the region-level negative predictive value of [F]CTT1057
- Evaluate the region-level accuracy of [F]CTT1057
- Detection of distant metastasis in PS patients
- Characterize the safety and tolerability of [F]CTT1057

- [F]CTT1057 scan inter-reader variability
- [F]CTT1057 scan intra-reader variability
- To further assess [F]CTT1057 pharmacokinetics in humans in a subset of approximately 10 patients

## 2.6.1 Secondary endpoint(s)

Secondary endpoints are defined for the EFF unless otherwise specified with details given as follows:

**Patient-level specificity** is defined as the proportion of TN participants among those who are TN or FP.

**Patient-level positive predictive value** is defined as the proportion of TP participants among those who are TP or FP.

**Patient-level negative predictive value** is defined as the proportion of TN participants among those who are TN or FN.

**Patient-level accuracy** is defined as the proportion of TP and TN participants among all participants in EFF (regardless of TP, TN, FP, FN)

where TP, TN, FP, FN participants are defined as follows:

- PSMA TP participants are those who show at least one pathological [F]CTT1057 uptake either in the primary tumor and/or metastatic PLNs with anatomically localized correspondence with the SoT, regardless of co-existing FP lesions in those two regions.
- PSMA TN participants are those who do not show any pathological [F]CTT1057 uptake neither in the primary tumor nor metastatic PLNs and will be confirmed NOT having primary tumor nor metastatic PLNs with the SoT.
- PSMA FP participants are those who are not TP and show at least one pathological [F]CTT1057 uptake either in the primary tumor and/or metastatic PLNs but will be verified NOT having primary tumor nor metastatic PLNs with the SoT or none of the lesions is correctly localized in anatomical location by the SoT.
- PSMA FN participants are those who do not show any pathological [F]CTT1057 uptake neither in the primary tumor nor metastatic PLNs but will be confirmed having primary tumor or metastatic PLNs with the SoT.

Number of TP, TN, FP, FN participants will be presented and used to calculate the diagnostic performance parameters.

Two-sided exact binomial 95% CIs for diagnostic performance parameters will be calculated.

**Region-level sensitivity** is defined as the proportion of TP PLN regions among those that are TP or FN.

**Region-level sensitivity** will also be presented, excluding PLNs showing metastasis < 2 mm (micro-metastasis).

**Region-level positive predictive value** is defined as the proportion of TP PLN regions among those that are TP or FP.

Novartis	Confidential	Page 24 of 43
SAP Amendment 2		Study No. CAAA405A12302

**Region-level negative predictive value** is defined as the proportion of TN PLN regions among those that are TN or FN.

**Region-level accuracy** is defined as the proportion of TP and TN PLN regions among those that are identified on [F]CTT1057 (regardless of TP, TN, FP, FN)

where TP, TN, FP, FN regions are defined as follows:

- PSMA TP regions are regions that test positive for PLN on [F]CTT1057 and confirmed positive on the SoT
- PSMA TN regions are regions that test negative for PLN on [F]CTT1057 and confirmed negative on the SoT
- PSMA FP regions are regions that test positive for PLN on [F]CTT1057 but verified negative on the SoT
- PSMA FN regions are regions that test negative for PLN on [F]CTT1057 but verified positive on the SoT

The number of TP, TN, FP, FN PLN regions will be presented and used to calculate the diagnostic performance parameters.

Two-sided exact binomial 95% CIs for diagnostic performance parameters will be calculated.

[F]CTT1057 scan inter-reader variability is defined as the agreement rate among reader determinations and will be assessed by Fleiss' Kappa statistic. See details given in Section 2.6.2.

[F]CTT1057 scan intra-reader variability is defined as the within-reader agreement rate and will be assessed by Cohen's Kappa statistic. See details given in Section 2.6.2.

**Detection number of distant metastasis** is defined as number of distant metastasis (extra-PLN, visceral or skeletal) identified at PET scan for each participant in all participants with an evaluable [F]CTT1057 PET/CT scan. Summary statistics will be provided by region, i.e. extra-PLN, visceral and skeletal.

**Detection rate of distant metastasis** is defined as **the** percentage of participants with at least one distant metastatic lesion (extra-PLN, visceral or skeletal) identified by PET scan in all participants with an evaluable [F]CTT1057 PET/CT scan. **Detection number of distant metastasis** will be presented and used to calculate **Detection rate of distant metastasis**, along with two-sided exact binomial 95% CIs for detection rate will be calculated.

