## 2 Objectives and endpoints

**Table 2-1 Objectives and related endpoints**

Objective(s)	Endpoint(s)
Primary objective(s)	Endpoint(s) for primary objective(s)

 
Evaluate the patient-level sensitivity of [F]CTT1057
 
	
 
Sensitivity of [F]CTT1057 PET imaging, considering PSMA positive patients as those who show at least one pathological
 

Objective(s)	Endpoint(s)
	[  F]CTT1057 uptake either in the primary tumor and/or metastatic PLN regions, with anatomically localized correspondence with the SoT. See Section 2.1 for Primary Estimand.

 
Evaluate the region-level specificity of [F]CTT1057
 
	
 
Specificity of [F]CTT1057 PET imaging, defined as proportion of PLN regions that test negative for lymph nodes on [F]CTT1057 among those that are lymph node negative on the SoT. See Section 2.1 for Primary Estimand.
 

Secondary objective(s)	Endpoint(s) for secondary objective(s)

 
Evaluate the patient-level specificity of [F]CTT1057
 
	
 
Specificity of [F]CTT1057 PET imaging, considering PSMA negative patients as those who do not show any pathological [F]CTT1057 uptake either in the primary tumor or PLNs and will be confirmed not having primary tumor or metastatic PLNs with the SoT
 

 
Evaluate the patient-level positive predictive value of [F]CTT1057
 
	
 
Proportion of patients who are both [F]CTT1057 and SoT positive (true positives (TP) among those who test positive on [F]CTT1057 (TP+ false positives(FP))
 

 
Evaluate the patient-level negative predictive value of [F]CTT1057
 
	
 
Proportion of patients who are both [F]CTT1057 and SoT negative (true negatives (TN)) among those who test negative on [F]CTT1057 (TN+ false negatives (FN))
 

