## **4 Rationale**

### **4.1 Rationale for study design**

In this study, a single-dose of the investigational PET imaging radiopharmaceutical [ $^{18}\text{F}$ ]CTT1057 will be administered intravenously, in an open-label single-arm design.

The most commonly used measures for evaluating the diagnostic performance of a new imaging modality are sensitivity and specificity. Histopathology of the tumor samples is considered as the SoT to assess the diagnostic performance of PET tracers targeting PSMA ([Maurer et al 2016](#), [Woythal et al 2018](#), [Kuten et al 2020](#)). In PS patients, both the primary tumor and the metastatic lymph nodes (LN) are expressing PSMA, which is the target for [ $^{18}\text{F}$ ]CTT1057 binding. Within a period of up to 6 weeks after completion of the [ $^{18}\text{F}$ ]CTT1057 PET/CT scan, patients will undergo surgery as per their standard of care treatment plan, consisting of RP and ePLND, as per the European Association of Urology (EAU) guidelines for Prostate Cancer 2020 (refer to [Section 16.1](#)).

In addition to the prostate dissection, a minimum of 12 PLN per patient will be dissected in order to have enough numbers of PLN in total for the calculation of the co-primary endpoints and the diagnostic performance yielding secondary endpoints.

Local pathologists with experience in PCa who will be blinded to the [F]CTT1057 PET/CT results will then assess the tissue specimens as per SoC. For the anatomical correspondence with PET/CT images, a sextant template will be used for the prostate (Kuten et al 2020). For the PLN, an anatomical side approach left/right will be used, since the borders of dissection are not usually very clear neither for the surgeon nor for the pathologist.

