## 5.1 Inclusion criteria

Participants eligible for inclusion in this study must meet **all** of the following criteria:

- 1a. Untreated high risk biopsy-proven PCa patients according to D'Amico classification (Stage  $\geq$  T2c or PSA level  $>20$ ng/ml or Gleason score  $\geq 8$ ) (D'Amico et al 1998)
2. Scheduled or planned radical prostatectomy and extended pelvic lymph node resection up to 6 weeks after the investigational PET/CT scan followed by histopathology assessment
3. ECOG performance status 0-2
4. Signed informed consent must be obtained prior to participation in the study
5. Participants must be adults  $\geq 18$  years of age

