### 6.2.2 Prohibited medication

Any medication that may interfere with PSMA PET imaging is not allowed. Prior to completing [F]CTT1057 PET/CT imaging and surgery, any ADT including LHRH analogues (agonists or antagonists) as well as anti-androgens (both first and second generation compounds) and 5-alpha reductase inhibitors are prohibited. Any therapy/procedure that could interfere with PET PSMA imaging is not allowed.

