### 8.3.3 Appropriateness of efficacy assessments

Histopathology of the tumor samples is considered as the SoT to assess the diagnostic performance of [F]CTT1057 PET agent. After surgery, pathology of the primary tumor and the dissected PLN will be used as SoT.

The assessment will be performed by the local pathologists with experience in PCa at each site, as per SoC, in order to mimic as much as possible the clinical situation. Pathologists will be blinded to the PET/CT scan results.

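### Patient-level specificity and NPV have essentially no true-negative men in a biopsy-proven prostatectomy population, so neither can be estimated informatively

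*SAP*

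**What the plan says.** Protocol Table 2-1 and SAP Table 1-1 list patient-level specificity and NPV among the secondary objectives. Table 2-1 describes the negative man as one with no pathological "uptake either in the primary tumor or PLNs and will be confirmed not having primary tumor or metastatic PLNs with the SoT". SAP 2.6.1 defines a true negative (TN) as a participant with uptake "neither in the primary tumor nor metastatic PLNs and will be confirmed NOT having primary tumor nor metastatic PLNs with the SoT". NPV "is defined as the proportion of TN participants among those who are TN or FN", and specificity is TN over TN plus FP. Exact two-sided 95% CIs are planned for both.

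The population and reference standard are fixed elsewhere:

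- Protocol 5.1 admits "Untreated high risk biopsy-proven PCa patients according to D'Amico classification" and requires "Scheduled or planned radical prostatectomy and extended pelvic lymph node resection".
- Protocol 5.2 excludes prior or current ADT and incidental cancer found after transurethral resection. Protocol 6.2.2 prohibits, until PET and surgery are complete, "any ADT including LHRH analogues (agonists or antagonists) as well as anti-androgens" and 5-alpha reductase inhibitors.
- Under Protocol 8.3.3, "pathology of the primary tumor and the dissected PLN will be used as SoT".
- SAP 2.2 limits the efficacy set to men with both an evaluable scan and a histopathology assessment.

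In SAP 2.6.1 the false-positive class also takes in men with cancer when none of their PET lesions is correctly localised. A man counts as TP even if he has false-positive lesions as well.

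**The concern.** A man can be SoT-negative only if pathology finds tumour in neither his prostate nor his nodes. Entry requires proven cancer, treatment that might shrink it before surgery is barred, and the specimen includes the prostate. The class on which specificity and NPV depend is therefore empty or nearly so by design. The 30% nodal prevalence used for the region-level calculation does not fill it, because a node-negative man with tumour in his prostate is still SoT-positive at patient level.

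If the plan is followed as written, the report may carry an NPV of 0% with a confidence interval. A reader would take that for a failing test, when it only restates the eligibility criteria. Neither Protocol 12.5.1 nor SAP 2.6 acknowledges this, gives an expected number of SoT-negative men, or says what to print when a denominator is zero.

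**Working it through.** **1. The plan's own figure.** SAP 3 requires at least 156 evaluable men. SAP 3.1 powers sensitivity on about 156 men with primary tumour and/or metastatic nodes: p0 = 0.50, p1 = 0.63, one-sided 2.5%. The exact binomial test succeeds at 91 or more of 156, with alpha 0.0225 and power 0.901. Enrolment is 156/0.80 = 195. Both figures reproduce. Planned SoT-negative men: 156 − 156 = 0.

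**2. With no SoT-negative men (TN = 0).**

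- NPV = TN/(TN + FN) = 0/FN. At sensitivity 0.63 with no mislocalised men, FN = 156 × 0.37 = 58. The Clopper-Pearson upper limit is 1 − 0.025^(1/FN).
  - 0/58: 0%, CI 0 to 6.2%
  - 0/20: 0%, CI 0 to 16.8%
  - 0/8 (sensitivity 0.95, 156 × 0.05 = 7.8): 0%, CI 0 to 36.9%
  - FN = 0: undefined
- The point estimate is the same for a tracer missing 58 men and one missing 8. Only the interval moves, and it is narrower for the worse tracer.
- Specificity = TN/(TN + FP) = 0/FP. Every FP man here is a man with cancer whose lesions were all mislocalised.
  - FP = 1: 0%, CI 0 to 97.5%
  - FP = 5: 0%, CI 0 to 52.2%
  - FP = 10: 0%, CI 0 to 30.8%
  - FP = 0: undefined
- Accuracy = (TP + TN)/N = TP/N.

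**3. If a few men are SoT-negative.** The documents give no rate q. The assumption is 0 to 1%; 2% and 5% are added as a stress range. The expected number is 156q, and P(none) = (1 − q)^156.

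| q | Expected | P(none) |
|---|---|---|
| 0.5% | 0.8 | 46% |
| 1% | 1.6 | 21% |
| 2% | 3.1 | 4% |
| 5% | 7.8 | <0.1% |

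Suppose k such men are all read negative (CIs in brackets):

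| k | Specificity, no FP | Specificity, 5 mislocalised men | NPV, FN = 58 | NPV, FN = 8 |
|---|---|---|---|---|
| 1 | 1/1 = 100% (2.5–100) | 1/6 = 16.7% (0.4–64.1) | 1/59 = 1.7% (0.04–9.1) | 1/9 = 11.1% (0.3–48.3) |
| 3 | 3/3 = 100% (29.2–100) | 3/8 = 37.5% (8.5–75.5) | 3/61 = 4.9% (1.0–13.7) | 3/11 = 27.3% (6.0–61.0) |

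If a single SoT-negative man is read positive instead and there are no other FP men, specificity is 0/1 = 0% (CI 0 to 97.5%). Even with 8 such men, all read negative, NPV is 8/66 = 12.1% with 58 FN and 8/16 = 50% with 8 FN.

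**4. The co-primary endpoints.** Patient-level sensitivity does not need SoT-negative men. Region-level specificity uses PLN regions; at 30% prevalence about 156 × 0.70 = 109 evaluable men are node-negative.

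**The case against.** The best defence is that little depends on these rows. They carry no hypothesis, threshold or role in study success (SAP 2.5.2 and 2.6.2). The TP, TN, FP and FN counts are to be presented, so an attentive reader would see TN = 0. The plan puts specificity at PLN-region level because enough negatives are expected there, and reports region-level NPV too. All of this is true, and it limits the harm to secondary results that could be misread. It does not make the two quantities measure what their names say.

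Three stronger readings are tempting and are not supported:

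- A reader might infer that both measures must come out at about 0% or undefined whatever the tracer does. That is exact only with no SoT-negative men. At an assumed 1% there is a 79% chance of at least one (100% − 21%), and a single one could give a specificity of 100%. The supported statement is that the measures are uninformative.
- A reader might infer that the trial has no measure of false-positive prostate uptake. It has a partial one: men whose lesions are all mislocalised count as FP and enter patient-level PPV, TP/(TP + FP). What goes uncounted is false-positive prostate uptake in men who are also TP.
- A reader might infer that the intervals will be misleadingly tight. The 0/58 interval is; 0/8 and the specificity examples are not.

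It is also fair to doubt that a sextant-level analysis is free. Protocol 4.1 says "For the anatomical correspondence with PET/CT images, a sextant template will be used for the prostate", but has central readers grade patients and regions 0 or 1, with the prostate as one region. The template appendix (Protocol 16.3) is titled for histopathology. Locating positive lesions does not require a recorded negative for every other sextant, and the imaging charter is not among the documents.

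**Conclusion.** The point stands as a defect in two secondary endpoints. On the plan's own numbers (156 of 156 evaluable men SoT-positive), NPV is 0% for any non-zero FN count and specificity is 0% or undefined, with a denominator that counts localisation errors among men with cancer. If the assumed 0 to 1% of men are SoT-negative, specificity can land anywhere from 0 to 100%, and NPV turns on one to three men and the FN count. Patient-level accuracy is about TP/N in every case. The conclusion that the class is essentially empty rests on the eligibility rules, the reference standard and the sample-size section; only the small rate is assumed. The missing class does not weaken the co-primary endpoints or the rule for study success.

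**What to change.** In SAP 1.2, 2.6.1 and 2.6.2, with SAP section 4 recording the departure from Protocol Table 2-1 and 12.5.1:

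1. State that patient-level specificity and NPV are not estimable as performance measures in this population.
2. For each reader, report the TP, TN, FP and FN counts and list any SoT-negative men, in place of percentages with CIs.
3. Show mislocalised men with cancer separately from SoT-negative FP men.
4. Label patient-level accuracy as having no informative negative class.
5. Rely on PLN-region specificity and NPV for performance on negatives.
6. Only if central reads already record PET findings by sextant, add prostate sextant-level specificity and NPV per reader, with CIs clustered by man. This would capture the false-positive prostate uptake in TP men that is otherwise not counted.

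Items 1 to 5 cost SAP wording and a table layout, with no new data. The price is that two listed secondary endpoints become descriptive counts. Item 6 is cheap only if the data exist, which the sponsor must confirm. Editing the protocol text itself would need an amendment under Protocol 14.1.
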